Exploratory Obj 1	Other pneumonia ²	Medical claim with an ICD-10 code in the inpatient, non-IP, or pharmacy setting for pneumonia other than adenoviral or cytomegaloviral pneumonia (dichotomous)	Index date to end of follow-up, where follow-up will be based on last dose of elranatamab or teclistamab (e.g., 14 days after last recorded dose or 90 days after last recorded dose).
Exploratory Obj 1	Upper respiratory tract Infection ²	Medical claim with an ICD-10 code in the inpatient, non-IP, or pharmacy setting for upper respiratory tract infection (dichotomous)	Index date to end of follow-up, where follow-up will be based on last dose of elranatamab or teclistamab (e.g., 14 days after last recorded dose or 90 days after last recorded dose).
Exploratory Obj 1	Sepsis ²	Medical claim with an ICD-10 code in the inpatient, non-IP, or pharmacy setting for sepsis (dichotomous)	Index date to end of follow-up, where follow-up will be based on last dose of elranatamab or teclistamab (e.g., 14 days after last recorded dose or 90 days after last recorded dose).
Exploratory Obj 1	Cytomegaloviral infection ²	Medical claim with an ICD-10 code in the inpatient, non-IP, or pharmacy setting for cytomegaloviral infection (dichotomous)	Index date to end of follow-up, where follow- up will be based on last dose of elranatamab or teclistamab (e.g., 14 days after last recorded dose or

			90 days after last recorded dose).
Exploratory Obj 1	PJP ²	Medical claim with an ICD-10 code for PJP (dichotomous)	Index date to end of follow-up, where follow-up will be based on last dose of elranatamab or teclistamab (e.g., 14 days after last recorded dose or 90 days after last recorded dose).
Exploratory Obj 1	Hepatitis C ²	Medical claim with an ICD-10 code in the inpatient, non-IP or pharmacy setting for hepatitis C (dichotomous)	Index date to end of follow-up, where follow-up will be based on last dose of elranatamab or teclistamab (e.g., 14 days after last recorded dose or 90 days after last recorded dose).
Exploratory Obj 1	Hepatitis B ²	Medical claim with an ICD-10 code in the inpatient, non-IP or pharmacy setting for hepatitis B (dichotomous)	Index date to end of follow-up, where follow-up will be based on last dose of elranatamab or teclistamab (e.g., 14 days after last recorded dose or 90 days after last recorded dose).

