Exploratory Obj 1	Other infectious hepatitis ²	Medical claim with an ICD-10 code in the inpatient, non-IP or pharmacy setting for infectious hepatitis (other than hepatitis B or C) (dichotomous)	Index date to end of follow-up, where follow-up will be based on last dose of elranatamab or teclistamab (e.g., 14 days after last recorded dose or 90 days after last recorded dose).
Exploratory Obj 1	Helicobacter pylori ²	Medical claim with an ICD-10 code in the inpatient, non-IP or pharmacy setting for helicobacter pylori (dichotomous)	Index date to end of follow-up, where follow-up will be based on last dose of elranatamab or teclistamab (e.g., 14 days after last recorded dose or 90 days after last recorded dose).

Exploratory Obj 1	Candida esophagitis ²	Medical claim with an ICD-10 code in the inpatient, non-IP or pharmacy setting for candida esophagitis (dichotomous)	Index date to end of follow-up, where follow-up will be based on last dose of elranatamab or teclistamab (e.g., 14 days after last recorded dose or 90 days after last recorded dose).				
Exploratory Obj 1	Urinary tract infection ²	Medical claim with an ICD-10 code in the inpatient, non-IP or pharmacy setting for a urinary tract infection (dichotomous)	Index date to end of follow-up, where follow-up will be based on last dose of elranatamab or teclistamab (e.g., 14 days after last recorded dose or 90 days after last recorded dose).				
Exploratory Obj 1	Time to infection onset	Time in days from index date to first infection for the following infections:	Index date until censor				
Effectiveness	Effectiveness						
Exploratory Obj 2	os	Time (in months) from index date until date of death (continuous)	Index date until censor				
Exploratory Obj 2	TTNT/D	Time (in months) from index date until the date of the next treatment (CAR-T, BsABs, bendamustine or belantamab) or death (continuous)	Index date until censor				

- 1. Variable will be measured as incident and prevalent. Incident cases have 30-day washout period applied
- 2. Variable will be measured as incident and prevalent. Incident cases have 60-day washout period applied
- 3. Variable will be measured as incident and prevalent. Incident cases have 14-day washout period applied

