Rash	Adverse events	Claims data	ICD-10 Diagnosis: R21, D72.12
Angioedema	Adverse events	Claims data	ICD-10 Diagnosis: T78.3X, D72.118
Erythema	Adverse events	Claims data	ICD-10 Diagnosis: L53.0, L53.1, L53.2, L51, L52, L71.0, L71.1, L71.8, L93.0, L93.2, L49.0, L49.1, L49.2, L49.3, L49.4, L49.5, L49.6, L49.7, L49.8, L49.9, L00, L26, L30.4, L53.8, L92.0, L95.1, L98.2, L53.9
Muscle spasms	Adverse events	Claims data	ICD-10 Diagnosis: M62.83X
Musculoskeletal pain	Adverse events	Claims data	ICD-10 Diagnosis: M25.50, M25.522, M25.551, M25.552, M25.561, M25.562, M25.572, M25.579, M25.59, M25.612, M25.621, M25.629, M25.631, M25.641, M25.642, M25.662, M25.669, M25.671, M25.673, M25.674, M25.675, M25.676, M54.6, M54.81, M79.1, M79.12, M79.18, M79.621, M79.622, M79.631, M79.639, M79.641, M79.644, M79.646, M79.669, M79.671, M79.673, M79.675, M25.511, M25.512, M25.519, M25.521, M25.529, M25.531, M25.532, M25.539, M25.541, M25.542, M25.549, M25.611, M25.619, M25.622, M25.632, M25.639, M25.649, M25.651, M25.659, M25.672, M25.69, M25.671, M25.69, M25.672, M25.69, M25.672, M25.69, M25.672, M27.69, M27.603, M79.604, M79.605, M79.606, M79.609, M79.629, M79.632, M79.672, M79.674, M79.676
COVID-19	Adverse event - infection	Claims data	ICD-10 Diagnosis: U07. 1

COVID-19 pneumonia	Adverse event -	Claims	ICD-10: J12.82
Adenoviral pneumonia	infection Adverse event - infection	data Claims data	ICD-10 Diagnosis: J12.0
Cytomegaloviral pneumonitis	Adverse event - infection	Claims data	ICD-10 Diagnosis: B25.0
Other pneumonia	Adverse event - infection	Claims data	ICD-10 Diagnosis: A01.03, A02.22, A20.2, A21.2, A31.0, A37.01, A37.11, A37.81, A37.91, A43.0, A48.1, B01.2, B05.2, B06.81, B37.1, B38.0, B38.2, B39.0, B39.2, B58.3, B59, B77.81, J10.00, J10.08, J11.00, J11.08, J12.1, J12.2, J12.3, J12.81, J12.89, J12.9, J13, J14, J15.0, J15.1, J15.20, J15.211, J15.212, J15.29, J15.3, J15.4, J15.5, J15.6, J15.7, J15.8, J15.9, J16.0, J16.8, J17, J18.0, J18.1, J18.8, J18.9, J85.1
Upper respiratory tract infection	Adverse event - infection	Claims data	ICD-10 Diagnosis: J20.9, J00.0, J04.0, J06.0, J06.9, J02.9
Sepsis	Adverse event - infection	Claims data	ICD-10 Diagnosis: A02.1, A32.1, A40.7, A40.0, A40.1, A40.3, A40.8, A41.9, A41.01, A41.02, A41.1, A41.2, A41.3, A41.4, A41.50, A41.51, A41.52, A41.53, A41.59, A41.81, A41.89, A42.9, A54.7, B37.86, R65.7, R65.20, A22.21, A26.7, A41.7, A41., A41.0, A41.5, P36.8, P36.0, P36.10, P36.19, P36.2, P36.30, P36.39, P36.4, P36.5, P36.8

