Cytomegaloviral infection	Adverse event - infection	Claims data	ICD-10 Diagnosis: B25.0, B25.1, B25.2, B25.8, B25.9, B27.0, B27.1, B27.2, B27.9
РЈР	Adverse event - infection	Claims data	ICD-10 Diagnosis: B59
Hepatitis C	Adverse event - infection	Claims data	ICD-10 Diagnosis: B17.1x, B18.2, B19.2x
Hepatitis B	Adverse event - infection	Claims data	ICD-10 Diagnosis: B16.x, B17.0, B18.0, B18.1, B19.1x
Other infectious hepatitis	Adverse event - infection	Claims data	ICD-10 Diagnosis: B17.2, B17.8, B17.9, B18.8, B18.9, B19.0, B19.9
Helicobacter pylori	Adverse event - infection	Claims data	ICD-10 Diagnosis: B96.81
Candida esophagitis	Adverse event - infection	Claims data	ICD-10 Diagnosis: B37.81
Urinary tract infection	Adverse event - infection	Claims data	ICD-10 Diagnosis: N39.0

Document Approval Record

Document Name:

C1071044_NON-INTERVENTIONAL STUDY PROTOCOL_V2_06AU G2025

Document Title:

C1071044_NON-INTERVENTIONAL STUDY PROTOCOL_V2_06AU G2025

Signed By:	Date(GMT)	Signing Capacity
Redacted	02-Sep-2025 15:50:58	Final Approval
Redacted	03-Sep-2025 15:07:21	Manager Approval

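### The closed Annex 2 code lists for Other infectious hepatitis and Other pneumonia do not fill the residual categories that Table 3 defines; hepatitis A is the clearest gap

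*Protocol*

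**What the plan says.** Section 9.3, Table 3, lists the infection outcomes under Exploratory Objective 1. Two are defined by what they exclude. Other pneumonia is "pneumonia other than adenoviral or cytomegaloviral pneumonia (dichotomous"). Other infectious hepatitis is "infectious hepatitis (other than hepatitis B or C) (dichotomous").

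Section 9.3 sends the reader to Annex 2 for the full code list. Section 9.8 says that measures will be coded from the codes and algorithms in the protocol and that the protocol will be followed strictly. The Annex 2 rows therefore decide what is counted.

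- The Other infectious hepatitis row is "B17.2, B17.8, B17.9, B18.8, B18.9, B19.0, B19.9", seven codes.
- The Other pneumonia row has 55 codes. Its fungal, parasitic and influenza part includes "B37.1, B38.0, B38.2, B39.0, B39.2, B58.3, B59, B77.81, J10.00, J10.08, J11.00, J11.08". Its bacterial part ends with "J15.3, J15.4, J15.5, J15.6, J15.7, J15.8, J15.9, J16.0, J16.8, J17, J18.0, J18.1, J18.8, J18.9, J85.1".

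The Annex 2 row for baseline Any infection has no codes of its own and points to the individual infection rows.

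**The concern.** A category defined by exclusion should catch whatever the named categories leave over. If its code list is closed and incomplete, the missing infections have no other row to fall into. The written definition then promises more than the programmed variable delivers, and a reader of the results tables could not tell.

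This matters because infections are a leading known harm of both drugs. Section 7 cites infections in 69.9% of elranatamab and 76.4% of teclistamab trial patients, and the abstract names infections among the adverse events to be reported. Those are all-infection rates and say nothing about the particular codes discussed here. They show only why the infection outcomes should mean what their definitions say.

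**Working it through.** The protocol gives no figure for this point, so the check compares the Table 3 definitions with every infection row of Annex 2. Annex 2 does not print code meanings; those used below are standard ICD-10 nomenclature, for the sponsor to confirm.

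**Hepatitis.** Codes printed in the three rows, by ICD-10 block:

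| Block | Hepatitis B row | Hepatitis C row | Other infectious hepatitis row |
|---|---|---|---|
| B15 | none | none | none |
| B16 | B16.x | none | none |
| B17 | .0 | .1x | .2, .8, .9 |
| B18 | .0, .1 | .2 | .8, .9 |
| B19 | .1x | .2x | .0, .9 |

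The rows share out blocks B16 to B19 between them, but B15 (hepatitis A) is in none, nor in any other infection row. Hepatitis A is an infectious hepatitis other than B or C, so it meets the Table 3 wording and is not counted.

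**Pulmonary mycoses.** The pneumonia row holds B37.1, B38.0, B38.2, B39.0, B39.2 and B59, so fungal lung infection is in scope. No code in B44 (aspergillosis), B45 (cryptococcosis) or B46 (mucormycosis) appears in any infection row. The protocol gives no reason for counting some and not others.

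**Influenza pneumonia.** Four codes are present: J10.00, J10.08, J11.00 and J11.08. J10.01 and the whole J09 block are absent.

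**Gram-negative pneumonia.** J15.0, J15.1, J15.5 and J15.6 are present. J15.6 is printed without a wildcard, and J15.61 and J15.69 are not printed. Whether they are captured depends on how codes are matched, and Annex 2 is not consistent on this:

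- Towards exact matching: wildcards are marked elsewhere with x (B16.x, B17.1x); the anemia row prints D59.3 beside D59.30, D59.31 and D59.39; and the pneumonia row itself spells out J15.20, J15.211, J15.212 and J15.29.
- Towards prefix matching: the non-hematological malignancy row prints a bare C50 among wildcarded blocks, and A41. and G64. appear with a trailing dot.

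**Effect on the estimates.** Section 9.7.6 defines prevalence as patients with an event divided by all patients in the cohort, times 100. Adding codes can only leave prevalence unchanged or raise it. Incidence need not move in one direction, because an added code found in the washout can also reclassify a patient as a baseline case.

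For scale only, Section 9.5 gives 133 patients with an elranatamab claim as of August 2024. At that size one missed patient changes a prevalence by 1/133 x 100 = 0.75 percentage points, and by less as the cohort grows. The protocol does not say how many patients would carry only an omitted code, so no estimate of the undercount follows.

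**The case against.** Most of the case on the other side is fair.

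- **The closed list is the operational definition.** Section 9.3 names Annex 2 as the full list, and Section 9.9 already declares misclassification by diagnosis codes as a limitation. That limitation concerns how providers code, however. It does not explain a list that fails to match the definition beside it.
- **B44 to B46 are a judgement.** Whether aspergillosis, cryptococcosis or mucormycosis counts as pneumonia is a choice that the protocol does not settle. This stands, and it is why rewording Table 3 is an acceptable alternative to adding those codes.
- **Few patients are affected.** Someone with an omitted code is still counted if any claim carries a listed one, such as J18.9 or J17. Baseline Any infection spans 17 types in Table 2 over the whole period since diagnosis, so one missing code will seldom change its yes or no value. Hepatitis A is expected to be rare. Section 9.9 expects a small sample and wide intervals, and the outcome is exploratory in a descriptive study. This stands as to size.
- **Influenza.** A reader might infer that influenza pneumonia is counted nowhere. It is not so: four influenza pneumonia codes are listed, and only J10.01 and J09 are missing.
- **J15.6.** A reader might infer that gram-negative pneumonia is lost for most of the study. The documents do not support this. Other gram-negative codes are listed, the protocol does not say that J15.6 was subdivided or when, and any loss needs exact matching, which is not stated. A share of calendar time would in any case not measure missed patients.

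**Conclusion.** The mismatch between definition and code list is real, specific and small. Hepatitis A meets the Table 3 definition and is in no row. The influenza part lacks J10.01 and J09. Pulmonary mycoses are covered unevenly without a stated reason. J15.6 is an item to verify, not a demonstrated error.

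The consequence is limited to patients whose only relevant code is an omitted one. They are missed in the two residual outcomes and, if they have no other listed infection code at baseline, in baseline Any infection. The size cannot be computed from the protocol; any percentage would rest on inputs it does not contain. The effect on time to infection onset cannot be judged either, because the list of infections for that variable is not legible in the text at hand.

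A reader might also infer that severe infection is under-reported. The protocol defines no severe-infection outcome: these variables are yes or no, without grade, and nothing in it shows that the omitted codes carry the severe cases.

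The conclusion assumes that the code meanings are the standard ones and that Annex 2 is applied as printed.

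**What to change.** In Annex 2:

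1. Add B15.x to the Other infectious hepatitis row.
2. Add J10.01 and J09.X1 to the Other pneumonia row.
3. Add B44.0, B44.1, B45.0 and B46.0 to the Other pneumonia row, or reword Table 3 so that the outcome is the listed pneumonias and not everything other than adenoviral and cytomegaloviral.
4. Check J15.6 against the code set in force during the study. Add J15.61 and J15.69, or print it as J15.6x, so that capture does not depend on the matching rule. One sentence saying whether unmarked codes match exactly or by prefix would settle this for the whole annex.

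Baseline Any infection picks up the changes through its reference to these rows.

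The cost is edits to two rows, or one row and a sentence in Table 3, plus a re-run, with no new data. Version 2.0 already amended Annex 2 for a daratumumab code and for intravenous anti-infectives, so there is precedent. Interim results produced under the old rows should be marked as such when set beside the final analysis planned for 27 February 2026.

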9.5. Study Size

As of August 2024, the dataset included 133 patients with a claim for elranatamab. To further assess whether sufficient sample size is available to proceed with the study, power analysis will be completed to assess estimates of precision for a one sample means considering either the elranatamab or teclistamab samples.

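### Table 3 and Annex 2 disagree on Other pneumonia: the code list keeps B59, the only PJP code, but omits COVID-19 pneumonia, which Table 3 does not exclude

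*Protocol*

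**What the plan says.** Under Exploratory Objective 1, Table 3 (Section 9.3) lists adenoviral pneumonia, cytomegaloviral pneumonitis, COVID-19 pneumonia, PJP and Other pneumonia as five separate yes/no outcomes. Each is reported as prevalent and incident, with a 60-day washout for incident cases (Table 3, note 2).

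- **Other pneumonia.** Table 3 words it as "pneumonia other than adenoviral or cytomegaloviral pneumonia (dichotomous". The Annex 2 list for it includes the run "B39.2, B58.3, B59, B77.81, J10.00".
- **PJP.** Table 3 has its own row: "Medical claim with an ICD-10 code for PJP (dichotomous". The whole Annex 2 entry is "ICD-10 Diagnosis: B59".
- **Cytomegaloviral infection.** Table 3 describes a claim in the "inpatient, non-IP, or pharmacy setting for cytomegaloviral infection (dichotomous". The Annex 2 list is "B25.0, B25.1, B25.2, B25.8, B25.9, B27.0, B27.1, B27.2, B27.9".

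Section 9.3 names Annex 2 as the full code list. Section 9.8 says that outcomes are programmed from the codes in the protocol and that the protocol is followed strictly. Section 9.7.6 defines prevalence as patients with the event over the cohort, and limits the incidence analysis to patients without the event before index.

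**The concern.** A category called Other, placed beside four named pneumonias, will be read as what is left after those four. The code list delivers that for three of them and not for PJP. The written definition does not settle the matter, because it names only two of the four exclusions. A programmer working from Annex 2 and a reader working from Table 3 would therefore describe different outcomes under one label. At stake is the meaning of the Other pneumonia prevalence and incidence in both the elranatamab and the teclistamab cohorts.

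The Cytomegaloviral infection row raises a smaller question of the same kind. Four of its nine codes come from a different ICD-10 category than the rest, while the Table 3 definition covers cytomegalovirus alone.

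**Working it through.** The protocol states no figure to reproduce. The check sets the code lists beside the definitions.

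**Step 1. The four named pneumonias against Other pneumonia.**

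| Separate outcome | Annex 2 code | Excluded by the Table 3 wording? | Left out of the Annex 2 Other pneumonia list? |
|---|---|---|---|
| Adenoviral pneumonia | J12.0 | yes | yes |
| Cytomegaloviral pneumonitis | B25.0 | yes | yes |
| COVID-19 pneumonia | J12.82 | no | yes |
| PJP | B59 | no | no |

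J12.82 is absent although its neighbours J12.1, J12.2, J12.3, J12.81, J12.89 and J12.9 are all listed. Two readings are possible:

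- Literal Table 3 wording: the list should hold both B59 and J12.82. It lacks J12.82.
- Residual reading (everything not named elsewhere): the list should hold neither. It contains B59.

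The list fits neither reading.

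**Step 2. Overlaps.** Other pneumonia has 55 codes. Intersecting the COVID-19, pneumonia, upper respiratory, cytomegaloviral and PJP lists pairwise gives two shared codes. One is B59, in Other pneumonia and PJP. The other is B25.0, in Cytomegaloviral pneumonitis and Cytomegaloviral infection. The second is a specific condition nested in a broader one and needs no change. Removing B59 leaves 54 codes in Other pneumonia and no overlap with PJP.

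**Step 3. Effect on the estimates.**

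- Prevalence: because B59 is the only PJP code, every PJP patient is also an Other pneumonia patient.
- Incidence, upward: a first PJP claim after index counts as incident Other pneumonia.
- Incidence, downward: a patient with PJP in the 60-day washout has a prior Other pneumonia event. A bacterial pneumonia after index then cannot count as incident.
- Unaffected: the PJP outcome itself, and the any-infection flag in Table 2, which already includes PJP and is set once per patient.

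**Step 4. Size.** No counts by code are given. For scale only, Section 9.5 states that "the dataset included 133 patients with a claim for elranatamab" as of August 2024. Per patient who qualifies only through B59, the addition to prevalence is 1/133 = 0.75 points. Three such patients give 3/133 = 2.26 points and five give 5/133 = 3.76 points.

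Section 9.4 bars direct reporting of cells of 1 to 10. At N = 133 that covers any PJP prevalence from 1/133 = 0.75% to 10/133 = 7.5%. A reader of the report would then have no PJP count with which to judge the overlap.

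**Step 5. Cytomegaloviral infection.** The row has 9 codes: five B25.x and four B27.x (B27.0, B27.1, B27.2, B27.9), so 4/9 = 44% lie outside B25.x. The protocol does not print what the B27.x codes mean. Whether each is specific to cytomegalovirus has to be read from the code book. After the check the row would hold between 5 and 9 codes.

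**The case against.** The best defence is that B59 does not breach the text. Table 3 excludes only adenoviral and cytomegaloviral pneumonia, so PJP falls within Other pneumonia as written. The outcomes are separate yes/no variables, nothing says that they are mutually exclusive or will be summed, and B25.0 also sits in two rows. All this is correct, so B59 cannot be called a coding error against the written definition. The defence does not clear the plan, because the same literal wording would put COVID-19 pneumonia in Other pneumonia, and Annex 2 leaves it out.

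Three stronger readings are tempting and are not supported:

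- *PJP is over-counted.* It is not. Its own row and code are unaffected.
- *Other pneumonia is inflated by 3 to 5 points.* This assumes a PJP rate of 3 to 5%: 0.03 × 133 = 4 to 0.05 × 133 = 7 patients. The protocol gives no PJP rate. The 133 is a count before eligibility criteria, and the study period has since been extended. The result is also a ceiling, since it requires that no PJP patient has any of the other 54 codes.
- *The cytomegaloviral row counts other infections as cytomegalovirus.* That depends on code meanings that the protocol does not give, so it can only be a request to verify.

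It is also fair that these are exploratory outcomes in a descriptive study, and that Section 9.9 already admits misclassification from diagnosis codes. That limitation concerns how providers code, however, not a mismatch between the protocol's own definition and its list.

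**Conclusion.** The inconsistency between Table 3 and Annex 2 on Other pneumonia is established from the protocol alone. Annex 2 omits one pneumonia that the definition allows (J12.82) and keeps the only code of another that is reported separately (B59). As programmed, every PJP claim counts under both outcomes, and PJP in the washout removes a patient from incident Other pneumonia, so incidence can move either way.

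Whether this is an over-count or an under-count depends on the intended definition. Against the residual reading, B59 adds cases; against the literal reading, the missing J12.82 removes them. The size is unknown: about 0.75 points per patient qualifying only through B59, under the assumption that N is 133. The point is minor and touches no primary objective. The B27.x codes stand as an item to verify, not as a demonstrated error.

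**What to change.** 1. In Annex 2, delete B59 from the Other pneumonia row and leave it in the PJP row.
2. In Table 3, reword Other pneumonia to pneumonia other than adenoviral, cytomegaloviral, COVID-19 or Pneumocystis pneumonia. Definition and list then agree, and J12.82 is correctly absent.
3. Check B27.0, B27.1, B27.2 and B27.9 against the ICD-10 code book. Keep in the Cytomegaloviral infection row only those specific to cytomegalovirus.

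The cost is one line of wording and a few codes, with no new data. Version 2.0 already amended Annex 2 for a mistyped drug code, so there is precedent. The change should be in place before the final analysis planned for 27 February 2026. Any interim tables of these outcomes produced with the present list should be rerun or footnoted, so that a change between data cuts is not mistaken for a change in infection rates.
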